13.4. NON-INVESTIGATIONAL MEDICINAL PRODUCTS

The research subject should be on a stable dosage for at least four weeks prior to the start of treatment (not ongoing dose changes) of at least one antidepressant. People with bipolar disorder should also be given a mood stabilizing drug.

To ensure that any clinical effect is dependent on pramipexole, it is recommended that study participants do not alter their ongoing antidepressant or mood stabilizing medication during the study. If the investigator, PAL or the patient himself assesses that the clinical condition nevertheless requires an adjustment of standing medication, this should of course be done. Nevertheless, the study participant can continue with pramipexole as planned, the change is noted in the patient's study log, and this is taken into account in the data analysis.

13.5 CONCOMITANT MEDICATION

Other drugs prescribed by the research subjects are managed as usual through their respective clinics. All concomitant medication is allowed while the research subjects are included in the study, except for those drugs that fall under exclusion criterion no. 11, i.e.:

- (i) ongoing treatment with medicinal products that affect plasma levels of pramipexole; For example, cimetidine, amantadine, mexilepine, zidovudine, cisplatin, quinine and procainamide.
- (ii) ongoing treatment with medicinal products that have a similar or antagonistic mechanism of action to pramipexole; For example, MAOIs, levodopa, other dopamine agonists, metoclopramide (Primperan), buspirone; This also applies to central stimulants such as methylphenidate and amphetamines (not caffeine).
- (iii) ongoing treatment with neuroleptics; For example, olanzapine, haloperidol, risperidone, clozapine, aripiprazole, quetiapine (Seroquel).

After a *wash-out* of > 14 days of all drugs, a patient can be included in the study.

14 METHODS FOR COLLECTING STUDY VARIABLES

The study variables are collected using estimation forms, routine clinical analysis of blood samples and with fMRI examination.

14.1 EFFICACY VARIABLES

Total score DARS (primary variable) and exploratory variables such as total score MADRS, SHAPS, MAP-SR, GAD-7, AES, *Fatigue Severity Scale* and *Insomnia Severity Index* gathered in a self-assessment questionnaire (validation of Swedish translation of DARS is in progress) at *screening-visit baseline*-visits and every other week for 10 weeks in connection with visit at the research clinic (a total of six occasions; MADRS and DARS on seven occasions).

Blood inflammation parameters (CRP, IL-6, TNF-alpha, and leukocytes) are collected at *baseline* and final visits. Other exploratory variables are collected during the fMRI examination.

14.2 SAFETY AND TOLERABILITY VARIABLES

14.2.1 Laboratory variables

Routine laboratory tests (blood tests) consist of eGFR, liver status (ASAT, ALAT, GT, ALP), Hb value and β-hCG and are taken between *screening* visits and *baseline* visits and at the final *visits*. Abnormal/unexpected/abnormal metrics after *screening* and termination visits are recorded and reported as incidents in the study. (see paragraph 15.5 below).

14.2.2. Vital metrics

Heart and lung status is performed according to the clinic's standard routine at screening visits. This includes anamnestic questions with direction against heart disease and auscultation of Cor/pulm. Blood pressure control is performed according to the clinic's standard routine at screening visits, v2, v4, v6, v8 and final visit (v10). Abnormal/unexpected/abnormal vital signs are recorded and reported as incidents in the study. (see paragraph 15.5 below).

14.2.3. Tolerability variables

Adverse reactions to pramipexole treatment are collected in connection with visits (biweekly physical visit and biweekly telephone contact). If adverse reactions develop between two visits, the research subject is asked to report this, and the strategy is usually to go back to the last tolerable dose and wait 7 days before making a new attempt at elevation (see section 13.3 for details).

15 SECURITY MONITORING AND REPORTING

15.1 DEFINITION OF INCIDENT

Term	Definition
Incident / Adverse Event (AE)	An undesirable medical event or deterioration of existing conditions in a research subject who has received a drug, and which is not necessarily causally related to the given treatment. Examples of incident: symptoms (nausea, somnolence, development of hypertension, development of mania).
Side effect / Adverse Reaction (AR)	An adverse medical event that is judged by a medically competent to have a reasonable probability of having a causal relationship with the study drug at any dose.
Serious Incident / Serious Adverse Event (SAE)	An undesirable medical event that meets one or more of the following criteria: 1. Death. 2. Life-threatening conditions. The term "life-threatening" refers to an event in which the participant was at risk of death at the time of the event. It does not refer to an event that hypothetically would have caused death if it were more serious. 3. Requires hospital care or prolongs an already started hospital session. 4. Causes a permanent or significant disability or disability. 5. Constitutes a congenital malformation or congenital defect. 6. Other medically significant event for the research subject that requires an intervention to prevent one of the above-mentioned criteria.
Serious adverse reaction Serious Adverse Reaction (SAR)	An adverse medical event that is both serious and is judged by a medically competent person to have a reasonable probability of having a causal relationship with the study medication.
SUSAR Suspected Unexpected Serious Adverse Reaction (SUSAR)	A suspected serious side effect that is unexpected, i.e. the nature and severity of which do not correspond to the known information on the medicine as specified in the reference safety information (Investigator's Leaflet [IB]) or Summary of Product Characteristics).

15.2 SAFETY INFORMATION

The Summary of Product Characteristics (SmPC) of pramipexole prolonged-release tablet (Orion Pharma) is used for the assessment of the relationship between the event and the medicine and the assessment of a suspected unexpected serious event (SUSAR).

15.3 ASSESSMENT OF SEVERITY

Mild: short-term/transient symptoms that do not affect the subject's daily activities.

Moderate: tangible/obvious symptoms that to some extent affect the research subject's daily activities.

Severe: symptoms that significantly affect the subject's daily activities.

15.4 INCIDENT RELATIONSHIP ASSESSMENT

Likely: good grounds and sufficient documentation to assume that a relationship between symptoms and study drug exists.

Possible: a possible causal relationship is conceivable and cannot be ignored.

Unlikely: symptoms that are unlikely to be related to the study drug.

15.5 REGISTRATION OF INCIDENTS

At each contact once a week (every other week physical visit and every other week telephone contact), the research subject will be asked how he/she has been feeling since the previous contact. The research subjects are also informed to report any incident between these visits for discussion of dose changes, among other things. Incidents are recorded in the research subject's medical record and in the study's CRF. Registration of difficulty and relationship is only done in CRF. As a minimum, a description of the event (diagnosis or symptoms), start and stop, relationship, severity, and if it is considered serious, measures and outcome are recorded for each incident.

Incidents are followed from the start of treatment until four weeks after the end of visits. If the research subject wishes to continue with pramipexole after the end of the study, this is done in consultation with the research subject's PAL. In such cases, no dosage decrease takes place, but incidents are followed up for four weeks after the final visit via telephone contact until it is completed or after two attempts with contact without results.

All serious incidents will be followed until they are recovered or no longer necessary to be followed.

15.6 PREGNANCY

Pregnant women will not be included in the study. Women of childbearing potential must have a negative serum β -hCG pregnancy test to rule out a pregnancy prior to initiation of treatment. Blood samples are taken between *screening* visits and *baseline* visits and at the final visit. Women who become pregnant during the study are excluded from the study. The effect of pramipexole on the unborn baby is unknown and treatment should be discontinued as early as possible. Clinical data are also lacking for pramipexole and breastfeeding, which is why ongoing breastfeeding is an exclusion criterion.

15.7 REPORTING OF INCIDENTS

15.7.1 Reporting of Incidents and Adverse Events

All incidents and adverse events are recorded by the trial site in the CRF during the study. Collected incidents and adverse events are reported at the end of the study through the final report to the authorities (see below).

15.7.2 Reporting of Serious Adverse Events and Serious Adverse Reactions (SAEs and SARs)

All serious incidents must be reported within 24 hours from knowledge to the investigator responsible and reported in the CRF. Reporting serious incidents and/or serious adverse reactions to the relevant authorities takes place annually through the annual safety report (see below)

15.7.3 Reporting of SUSARs – serious unexpected serious adverse reactions

A suspicious, serious unexpected adverse reaction to the study drug, SUSAR, that is fatal or life-threatening is reported to LV and EPM within 7 days of the event being detected. Supplementation of the report is sent to the authorities within a maximum of 8 days.

A suspicious, serious unexpected adverse reaction to the study drug, SUSAR, that is not fatal or life-threatening is reported to LV and EPM within 15 days of becoming aware of the event. A supplement to the report will be sent to the authorities as soon as possible.

15.8 ANNUAL SAFETY REPORT

The annual safety report is compiled by investigators and sent to LV and EPM, if EPM so wishes. The report summarizes serious incidents that have occurred, as well as a summary assessment of the safety of the research subjects who are still included in the trial, and whether the study's benefit-risk assessment has changed since the study was approved.

16 STATISTICAL CONSIDERATIONS

16.1 POWER CALCULATION

Fifteen individuals ($n = 15$) are included in the study to ensure that at least ten individuals complete the study (the number of *dropouts* is estimated to be less than one-third). No clinical study has previously used DARS as a primary efficacy variable, but during the development of DARS, the mean standard deviation (SD) was 13.73 when estimating depressed patients²⁹. Power calculation with 10 research subjects ($r = 0.5$, $\alpha = .05$) results in a difference in mean value of 16.6 at *power* 95% can be detected. This corresponds to the research subject estimating one point less on each question in DARS (a total of 17 questions), which would be a clear clinical improvement.

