11 STUDY POPULATION

Fifteen research subjects with either unipolar depression, bipolar disorder in depressive phase, or dysthymia are recruited to receive pramipexole treatment. All research subjects are asked to participate in the substudy (fMRI examination). Patients from the outpatient clinics and inpatient wards at the psychiatry in Lund will be asked if they want to participate in the study by treating physicians. Only those who are cared for under the Health and Medical Services Act (i.e. not under compulsory care) may be considered for the study. After the patient has been informed of the study and given consent, the patient will be invited to *screening* visits to the doctor responsible for research at the research clinic or the research physician visits the patient in the ward where the patient is admitted. All examinations/visits in connection with the study will take place at the adult psychiatry in Lund, while the fMRI examination will take place at Skåne University Hospital in Lund.

Research subjects who meet all inclusion criteria and no exclusion criteria as set out below, may be included in this study.

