16.2 POPULATION

Complete Analysis Quantity (FAS) is the primary analysis set. The analyses will also be performed on per protocol amount (PPS).

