16.3 STATISTICAL ANALYSIS OF PRIMARY, SECONDARY AND EXPLORATORY VARIABLES

All statistical analysis is performed using the IBM SPSS Statistics v24 software. Paired T-test (2-tailed) is used to analyze the difference in DARS scores between *baseline* and after ten weeks of treatment with pramipexole (primary variable). Normal distribution is expected based on previous studies. Descriptive analysis is performed by response (reduction by at least 50% in MADRS score), remission (MADRS ≤ 10 at study end) of depression symptoms (secondary variable), and number of *dropouts*. Descriptive analysis, mean and *range*, is performed on the dosage of pramipexole at the end of the visit. Of the exploratory variables, similar *paired* T-tests (or equivalent non-parametric method if necessary) are used for the analysis of difference in total scores MADRS, SHAPS, MAP-SR, AES, GAD-7, Fatigue Severity Scale and Insomnia Severity Index.

Analyses may also be made on imputed datasets. If values are missing from the measurements over time, they will be replaced with the means of adjacent values before and after the missing value or with the last observation.

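### Section 16.1: fifteen enrolled gives ten completers on average at one-third dropout, not for certain, and ten give 92.4% power for 16.6 DARS points, not 95%

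*Combined protocol and SAP*

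**What the plan says.** Section 11 fixes enrolment: "Fifteen research subjects with either unipolar depression, bipolar disorder in depressive phase, or dysthymia are recruited to receive pramipexole treatment". Section 16.1 gives the reason for that number, "to ensure that at least ten individuals complete the study", and adds that the number of dropouts "is estimated to be less than one-third".

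The same section then gives its only power statement. It opens "Power calculation with 10 research subjects", uses correlation 0.5 and alpha 0.05, and relies on scale-development data in which "the mean standard deviation (SD) was 13.73 when estimating depressed patients". The calculation "results in a difference in mean value of 16.6 at" 95% power, which the section likens to one point on each of the 17 DARS items.

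The test is named in section 16.3: "Paired T-test (2-tailed) is used to analyze the difference in DARS scores". Section 16.2 states that "Complete Analysis Quantity (FAS) is the primary analysis set" but does not define that set. Section 16.3 allows imputation (adjacent values or last observation) as a possible additional analysis.

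**The concern.** Two statements in section 16.1 are firmer than the design supports.

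- **Completers.** Dividing ten by two-thirds gives fifteen. That makes ten the expected number of completers at the dropout limit, not a minimum. The documents contain no rule for replacing dropouts, no point estimate of the rate and no stated basis for the limit. The number of dropouts is itself an outcome of the pilot (sections 9.3 and 16.3).
- **Power.** The pair of 16.6 points and 95% at ten subjects should follow from the stated inputs and the planned test, and it does not.

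At stake is how accurately the plan describes what it can detect. The pilot is also meant to inform the sample size of a larger randomized trial, so the same inflation and calculation could be carried forward.

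**Working it through.** **Inputs.** Section 11: 15 enrolled. Section 16.1: at least 10 completers, dropout below one-third, SD 13.73, r = 0.5, alpha 0.05, detectable difference 16.6 at 95% power, n = 10. Section 16.3: two-sided paired t-test.

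**1. The enrolment figure reproduces.** 10 / (1 − 1/3) = 15. Equivalently, 15 × 2/3 = 10 expected completers.

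**2. The power figure does not.** SD of the change = 13.73 × √(2 × (1 − 0.5)) = 13.73. Standardised difference = 16.6 / 13.73 = 1.209. With n = 10, the noncentrality parameter is 1.209 × √10 = 3.82 on 9 degrees of freedom. Exact two-sided power from the noncentral t distribution is 92.4%.

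Other readings of the calculation do not recover 16.6 at n = 10 either. A two-sided normal approximation and a one-sided t-test each give 96.9% power for 16.6, but their 95%-power differences are 15.7 and 15.5. Sixteen point six does match eleven subjects under the planned test.

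**3. Power and detectable difference by number analysed (planned test).**

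| Analysed | Power for 16.6 | Detectable at 95% power |
|---|---|---|
| 7 | 76.0% | 22.7 |
| 8 | 83.3% | 20.5 |
| 9 | 88.7% | 18.9 |
| 10 | 92.4% | 17.7 |
| 11 | 95.0% | 16.6 |
| 12 | 96.7% | 15.7 |
| 15 | 99.1% | 13.8 |

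For the one-point-per-item benchmark of 17 points, ten subjects give 93.5% power.

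**4. Chance of ten completers.** Assume that each participant drops out independently with the same probability d. The number completing is then Binomial(15, 1 − d), and the chance of interest is P(X ≥ 10). Average power is the sum over k of P(X = k) × power with k analysed. It takes the analysed number to be the number of completers.

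| Dropout d | P(at least 10 of 15) | Average power for 16.6 |
|---|---|---|
| 20% | 93.9% | 95.9% |
| 25% | 85.2% | 94.3% |
| 30% | 72.2% | 92.1% |
| one-third | 61.8% | 90.3% |

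**5. Splitting the shortfall at the boundary.** From the stated 95% to 90.3% is 4.7 points. Of these, 95 − 92.4 = 2.6 come from the calculation at n = 10 and 92.4 − 90.3 = 2.1 from attrition.

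**The case against.** The strongest defence is that the plan does not assume one-third dropout; it assumes less. Read as a count, fewer than one-third of fifteen means at most four dropouts, so at least eleven complete and ten follows with no probability involved. That is fair to the sentence. It also means that 62% is the edge of the assumption and not its centre. What remains is that the assumption carries the whole assurance. A rate expected to be below one-third does not fix the realised count, and at 25% dropout there is still a 15% chance of fewer than ten completers.

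A second defence is that completers need not equal the number analysed. DARS is recorded every two weeks, and last-observation imputation could bring early leavers into the full analysis set. With all fifteen analysed, power for 16.6 is about 99%. This cannot be ruled out, but the set is undefined, imputation is optional, and section 16.1 bases its power on the ten it expects to complete.

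A reader might infer something stronger: that the trial is underpowered, that it has only a 62% chance of delivering its design, or that more participants are needed. The documents do not support this. The plan excludes the one-third rate. Average power is still 90.3% at that rate, and at 25% dropout or below it exceeds the 92.4% given by exactly ten subjects. This is an open-label proof-of-concept pilot with estimation aims.

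**Conclusion.** Both statements in section 16.1 need correcting, and the point is minor. The power figure is wrong for the planned test whatever the dropout: 92.4% in place of 95%, or 17.7 points in place of 16.6. That conclusion rests only on the plan's own SD, correlation, alpha and test. The promise of ten completers is an expectation under an assumed dropout limit. The probabilities from 94% down to 62% depend on independent dropouts with a common rate, and the documents give no figure for that rate beyond its upper limit. Attrition costs about 2 points of average power at the boundary, relative to exactly ten subjects.

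**What to change.** Reword section 16.1 in two places.

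- Replace the assurance with a statement that fifteen enrolled is *expected to give at least ten completers if dropout is below one-third*. Add the chance of reaching ten at 20%, 25%, 30% and one-third dropout (94%, 85%, 72%, 62%), and say that independence is assumed.
- Replace the single figure of 16.6 at 95% power with the 95%-power detectable differences by number analysed: 20.5 at 8, 18.9 at 9, 17.7 at 10, 16.6 at 11, 15.7 at 12 and 13.8 at 15.

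The cost is a few sentences. Enrolment, procedures and the primary analysis do not change. The stated figures become slightly less favourable.

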Study population	
Inclusion (not exhaustive list): Age between 18 years and 75 years Diagnosis of unipolar depressive episode, bipolar disorder in depressive phase or dysthymia. Moderate to severe depression but with pronounced symptoms of anhedonia. To be able to participate, you must have an ongoing stable treatment with at least an antidepressant/mood stabilizer for at least 4 weeks.
 
Exclusion (not exhaustive list): Current pregnancy, breastfeeding or planned pregnancy. High suicidal. Substance abuse. Psychotic disorder. Compulsory treatment (LPT). Impulse control disorder. Diagnosis of moderate/severe renal failure or severe cardiovascular disease. Recently started psychotherapy. Ongoing ECT treatment.

Study design	
Proof of concept study, in which fifteen research subjects are included and receive study treatment (no placebo or control group occurs). All included research subjects will also be asked to participate in the substudy for fMRI examination before and after 10 weeks of treatment with pramipexole.

Timetable	
Study start: 1 September 2019 Study end: 1 December 2020.

Statistical considerations	
The objective of the study is to demonstrate feasibility (proof of concept) and we hope to generate preliminary data that will form the basis for a larger, definitive, randomized controlled trial. Specifically, we are interested in investigating: i) can we pick up a signal in our material that pramipexole has an anti-anhedonic effect in this study population, (ii) if the treatment doses we propose are reasonable: treatment effect versus side effects, iii) what the distribution looks like for DARS before and after treatment in order to optimize future dimension calculations.

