11.1 ELIGIBILITY CRITERIA

11.1.1 Inclusion criteria

1. Age ≥ 18 years ≤ 75 years.
2. Diagnosis of; unipolar depressive episode or bipolar disorder in depressive phase or dysthymia.
3. Depression symptoms: total score ≥ 18 , as measured by the Montgomery-Åsberg Depression Rating Scale (MADRS).
4. Anhedonia symptoms: total score < 27 , as measured by the Dimensional Anhedonia Rating Scale (DARS). (Low score = high level of anhedonia symptoms)
5. Have an ongoing treatment of at least one antidepressant medication ≥ 4 weeks without a dose change. For patients with bipolar disorder, there must also be ongoing treatment with mood-stabilizing drugs.
6. The research subject has signed informed consent to participate in the study.

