The tablets are usually taken at night if the research subject does not have sleep problems. If non-tolerable side effects occur in connection with an increase in dose, the research subject is encouraged to notify this and return to the dosage that did not cause side effects. After that, wait another seven days before a new attempt at dose increase occurs. This is done on a maximum of two occasions before giving up attempts to reach a higher dosage (treatment continues with the lower dosage if possible). An exception to this strategy is if the study participant experiences side effects in the form of impulse control disorder (e.g. pathological gambling addiction or compulsive buying behavior), manic state, or symptoms of heart failure. If such a situation arise, pramipexole will be tapered off and discontinued. Study participants will be assessed with YMRS at baseline, week 2, week 4, week 6, week 8 as well as at week 10 to evaluate any manic symptoms.

The total duration of treatment is ten weeks before an evaluation of efficacy is made and a decision is made on continued treatment or discontinuation (referral is sent to PAL, which is responsible for continued treatment with pramipexole). If the research subject during the study shows a 50% decrease on MADRS or a 50% increase on DARS (=response), further dose increase is stopped, and the research subject then remains on this dose for the rest of the study. Control of *compliance* This is done by asking the research subject to bring the remaining tablets (and dosage diary) to the evaluation visits every two weeks for control counting of the number of tablets.

Pramipexole treatment must not be stopped abruptly due to the risk of dopamine *agonist withdrawal syndrome* (DAWS) with symptoms such as depression, anhedonia, apathy, anxiety, sleep disturbances, and others. The study participant is carefully informed about this. If discontinuation of the drug becomes necessary, this will be done gradually as instructed in FASS: The pramipexole dose is gradually reduced by 0.75 mg of salt per day until the daily dose is reduced to 0.75 mg of salt. The dose should then be reduced by 0.375 mg of salt per day. The patient is instructed to report any withdrawal side effects and then the dose reduction can be individualized to counter them.

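### Section 16.1's 16.6-point DARS difference has 92.4% power, not 95%, with ten completers (95% needs 17.7), and the section describes improvement as a lower DARS score

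*Combined protocol and SAP*

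**What the plan says.** Section 16.1 enrols fifteen subjects "to ensure that at least ten individuals complete the study". It takes an SD of 13.73 from the development of the DARS in depressed patients. The calculation is introduced as "Power calculation with 10 research subjects", with r = 0.5 and alpha .05, and it "results in a difference in mean value of 16.6 at" 95% power. Section 16.1 does not state whether the test is one- or two-sided. Section 16.3 does: "Paired T-test (2-tailed) is used to analyze the difference in DARS scores between" baseline and ten weeks.

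Section 16.1 then gives the difference a clinical meaning: "This corresponds to the research subject estimating one point less on each question in DARS (a total of 17 questions"), which it regards as a clear clinical improvement.

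Two other places fix the direction of the scale. Inclusion criterion 4 in section 11.1.1 notes: "Low score = high level of anhedonia symptoms". Section 13.3 stops dose escalation when a subject "shows a 50% decrease on MADRS or a 50% increase on DARS (=response").

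**The concern.** Section 16.1 contains the only power statement behind the sample size, and it prints every input needed to repeat the calculation. Its result should therefore follow from those inputs and from the test named in section 16.3. It does not: at ten completers the stated power is too high for the stated difference.

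Separately, the sentence that explains what the detectable difference means to a patient points the wrong way. Under the protocol's own scoring, one point less on every question is a worsening of anhedonia on the primary variable.

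The pilot is meant to lead to a larger randomised trial, so readers will look at how it was sized. A power figure that cannot be reproduced and a reversed description of the primary scale invite criticism that is easy to avoid.

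**Working it through.** **Inputs.** From section 16.1: n = 10 completers, SD = 13.73, r = 0.5, alpha = .05, stated difference 16.6, stated power 95%, 17 questions. From section 16.3: paired t-test, two-tailed. Two assumptions are needed because section 16.1 does not spell them out: r is the correlation between baseline and week 10, and the SD is the same at both visits.

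**SD of the change.** SD_diff = SD × √(2(1 − r)) = 13.73 × √(2 × 0.5) = 13.73.

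**Trying to reproduce 16.6.** Under a noncentral t distribution with df = n − 1 = 9:

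- Standard error of the mean change = 13.73/√10 = 4.342.
- Two-sided critical value t(0.975, 9) = 2.262.
- Noncentrality at 16.6 points = 16.6/4.342 = 3.823, so power = 92.4%. A simulation of 1,000,000 trials also gives 92.4%.
- Solving for 95% power gives a difference of 17.66. This is 6.4% above 16.6.
- At 17 points (one point on each of 17 questions), power is 93.5%.

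**Other routes at n = 10, difference detectable with 95% power.**

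| Calculation | Difference |
|---|---|
| Two-sided paired t, df = 9 (the planned test) | 17.66 |
| One-sided paired t | 15.52 |
| Two-sided normal approximation | 15.65 |
| One-sided normal approximation | 14.28 |

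None gives 16.6. Figures close to it come from 11 pairs (16.61), from 10 pairs with 18 instead of 9 degrees of freedom (16.56), or from 9 pairs one-sided (16.55). Each departs from the stated n or the planned test, and the documents do not show which, if any, was used.

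**Effect of the number of completers (two-sided, SD_diff = 13.73).**

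| Completers | Detectable with 95% power | Power at 16.6 |
|---|---|---|
| 10 | 17.66 | 92.4% |
| 11 | 16.61 | 95.0% |
| 12 | 15.74 | 96.7% |
| 13 | 14.99 | 97.9% |
| 14 | 14.34 | 98.6% |
| 15 | 13.76 | 99.1% |

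**Effect of r (n = 10).**

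| r | SD_diff | Power at 16.6 | Detectable with 95% power |
|---|---|---|---|
| 0.3 | 16.25 | 82% | 20.9 |
| 0.5 | 13.73 | 92.4% | 17.7 |
| 0.56 | 12.9 | 95% | 16.6 |
| 0.7 | 10.64 | 99% | 13.7 |

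The choice of r, for which section 16.1 gives no source, moves the answer more than the slip does.

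**Points per question.** 16.6/17 = 0.98 and 17.66/17 = 1.04. Both are about one point per question, so the clinical anchor survives the correction.

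**Direction.** Sections 11.1.1 and 13.3 agree that a higher DARS score is better: low means more anhedonia, and response is an increase. Only section 16.1 has improvement as a lower score. No calculation is needed to see the conflict.

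**The case against.** The strongest reply concerns the equal-SD assumption. Inclusion criterion 4 admits only patients with DARS below 27. If scores are non-negative integers (the documents give no scale minimum), values from 0 to 26 cannot have a population SD above 13, and that maximum needs half the patients at each extreme. A baseline SD of 13.73 is therefore implausible. With SD_diff = √(SD₁² + SD₂² − 2·r·SD₁·SD₂), week-10 SD 13.73 and r = 0.5, a baseline SD of 5 gives SD_diff 12.04 and 97.1% power at 16.6, and a baseline SD of 11 gives 12.59 and 95.9%. On that view 16.6 is not optimistic for these patients.

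This is a fair point about the true power, but it does not rescue the printed figure. It replaces the stated SD with values the documents do not contain. A restricted baseline range may also lower r: at r = 0.4, power is 95.9% for a baseline SD of 5 but 92.4% for 11, and at r = 0.3 with a baseline SD of 5 it is 94.4%. The argument can go either way.

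Other parts of the objection stand and limit the importance of the point. Ten completers is a floor. Dropout strictly below one-third of 15 means at most 4 dropouts, hence at least 11 completers and 95.0% power. The primary set in section 16.2 is the full analysis set, and section 16.3 allows analyses on imputed data, so the number analysed may exceed ten. The direction slip has no analytic effect, because the test is two-tailed and the operative rules are worded correctly.

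**Conclusion.** The concern holds, at minor importance. With section 16.1's own inputs and section 16.3's test, ten completers give 92.4% power at 16.6 points, and 95% power requires 17.7. The shortfall is 2.6 percentage points, or about one DARS point. This rests on reading r as the baseline to week-10 correlation and on equal SDs at the two visits, which is the natural reading of a paired calculation that prints one SD and one r.

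The sample size remains adequate by the plan's own standard: power stays above 90% at the ten-completer floor. The error does not carry forward either, because the synopsis bases later sizing on observing "what the distribution looks like for DARS before and after treatment in order to optimize future dimension calculations".

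The wording of improvement as a lower score contradicts sections 11.1.1 and 13.3 and is wrong as written, without consequence for any criterion or test. Both are text corrections, not design problems.

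**What to change.** Restate the result in section 16.1 along these lines: with 10 completers, SD 13.73 at both visits, a baseline to week-10 correlation of 0.5 and two-sided alpha 0.05, a mean DARS increase of 17.7 points is detectable with 95% power (16.6 points with 92%). In the next sentence, change *less* to *more*; the comparison with about one point per question can stay.

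Optionally, add a line giving the range for r from 0.3 to 0.7 (detectable difference 20.9 down to 13.7 at n = 10), since the chosen value has no stated source.

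The cost is protocol wording only. There are no extra patients and no change to criteria, test or conduct. The one downside is a slightly less favourable stated figure.
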